Patients who are colonized with MRSA and who reside locally to the medical treatment facility and are able to return to the clinic will have repeat swabs (five swabs from sites listed above) every month (+/- 7 days). A month will be specifically defined as 28 days. Those who have repeat positive colonization swabs during this initial 6 month follow-up period will be observed. This data will assess the efficacy of decolonization procedures on MRSA carriage rates. Patients who are not local to the clinic will not have these repeat swabs performed, but rather will be seen at the next scheduled 6 month study visit. Adherence to the study medications will be assessed at the next scheduled study visit by a patient questionnaire (refer to case report forms). Each time a patient has a positive isolate for MRSA or MSSA, this will be frozen and saved for molecular analysis to determine the most common molecular types colonizing HIV patients and to determine if patients acquire new strains or remain colonized with the same strain over time.

All study patients (both those initially found to be colonized with MRSA and those with negative colonization swabs) will be re-evaluated in six month intervals ($+/- 2$ months) until the end of the study. Patients found to be positive at these subsequent 6 month intervals, will be randomized again, treated and followed as described above. During the last study visit (at the 2-year time period), patients will have swabs, but not undergo randomization. Hence, every 6 months, patients positive during that visit for MRSA colonization will be re-randomized in a 1:1 double-blinded fashion to mupirocin (Bactroban®) nasal ointment twice daily for seven days plus hexachlorophene (pHisoHex®) washes with showering once daily for seven days or to a placebo nasal ointment (white petroleum) and a placebo body soap with no antimicrobial activity for seven days. Repeat randomization will occur every 6 months for those carrying MRSA. For example, some patients initially randomized to receive Bactroban® and pHisoHex®, may later be randomized to the placebo arm, and vice versa.

Begin at the top of diagram again every 6 months ($+/- 2$ months). If patient is found to be positive on swabs, they are re-randomized to one of the two treatment groups for every 6-month positive swab.

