- (2) Is the treatment effect different for repeat administrations of hexachlorophene/mupirocin? The rate of MRSA positive versus negative for recolonization reoccurrence through the sequence 1 versus 2 versus 3 versus 4 treatments will be assessed by a test of trend.
- (3) Is there a persistent or repeated-treatment effect? The overall rates of MRSA recolonization at 6, 12, 18, and 24 months will be assessed by a test of trend.
- (4) Is there an individual propensity for susceptibility and what are the treatment differences between placebo and hexachlorophene/mupirocin in terms of length of time for being negative for MRSA colonization on repeated testing? A Kaplan-Meier long-rank test will be conducted on three groups: initially negative, initially positive treated with hexachlorophene/mupirocin, and initially positive treated with placebo, where survival is defined as not having acquired MRSA.

For the secondary objectives, part (a) will be assessments of the rates in which prevalence is defined as the number of patients colonized with MRSA at the beginning of

the study divided by the total population studied, and the incidence as the number of new infections per calendar time divided by the total population studied. For objective (b) examining for predictors of MRSA, we will create a multivariate logistic regression model and use a backward stepwise approach. For part (c), to evaluate if there is a significant change in the CD4 count and/or viral load pre- versus during a MRSA infection we will utilize a 1-way ANOVA. We will also compare pre-MRSA infection with after MRSA resolution as well as the counts during the infection with those after resolution. Finally, objective (d) will be a descriptive analysis of the molecular and microbiologic characteristics of the isolates. The main statistical data from the retrospective chart review study of HIV patients at NMCSD will be presented by descriptive analyses. We will compare demographics and HIV clinical data between those with and without MRSA using rank sum tests and Fisher's exact tests depending on the variable characteristics (categorical or continuous). A multivariate logistic regression model for predictors of MRSA will then be developed using a backward stepwise approach using Stata software.

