The sample size calculation for this study is based on the primary objective of the study which is to evaluate the effectiveness of decolonization procedures with application of nasal mupirocin (Bactroban®) and hexachlorophene (pHisoHex®) soaps compared to placebos with no antibacterial activity among patients found to be colonized with MRSA in the prevention of future colonization with MRSA. We will also examine the number of infections with MRSA and soft tissue infections as secondary measures of the primary objective.

The rate of MRSA colonization of the nares was 1% in a recent study involving the general US population [41]. Among HIV-infected patients this rate is higher, with one study showing a carriage rate of 27.6% [11]. However, other studies had rates of 3-9% among their HIV-infected patients [26, 27, 42]. The MRSA infection rate among HIV-infected persons is approximately 13 cases/1000 person-years in one study that examined 3,455 patients over three years with 94 MRSA infections [7]; our rate at NMCSD appears higher with 40 cases/1000 persons in the year 2005 [12].

In a study examining both MSSA and MRSA colonization rates, after treatment with mupirocin (Bactroban®), colonization was eradicated in 93%, whereas 85% who received placebo remained colonized ($P < .001$). At day 90 after study entry, 61% of the residents in the mupirocin group remained decolonized [36]. In a study by Ellis et al involving 812 soldiers over a 8-10 week period of training, of those with MRSA colonization without treatment for decolonization, 38% developed a soft tissue infection [43].

Using these data, assuming 10% of the HIV patients would be colonized, that half would be randomized to each treatment group, and that 85% in the non-treatment arm would remain colonized versus 7-39% (mean 23%) of the treated would remain colonized, we calculated the following sample sizes:

Colonization rate of the	Power	Alpha level	Sample size per group	Total sample size
--------------------------	-------	-------------	-----------------------	-------------------

Treated Group				
0.07	.80	.05	80	160
0.23	.80	.05	120	240
0.39	.80	.05	210	420

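### Question (4) sets no time zero and no re-randomization rule for patients who start positive; under one open reading the active v placebo contrast is heavily diluted

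*Combined protocol and SAP*

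**What the plan says.** Section VII (Statistical Analyses) lists four primary questions. Question (4) asks about treatment differences in "length of time for being negative for MRSA colonization on repeated testing". It plans a Kaplan-Meier log-rank comparison of three groups, "initially negative, initially positive treated with hexachlorophene/mupirocin, and initially positive treated with placebo", "where survival is defined as not having acquired MRSA".

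Section 6.3 describes treatment over time:
- "Patients found to be positive at these subsequent 6 month intervals, will be randomized again, treated and followed as described above". The new assignment is again 1:1.
- The protocol expects switching: "some patients initially randomized to receive Bactroban® and pHisoHex®, may later be randomized to the placebo arm, and vice versa".
- "During the last study visit (at the 2-year time period), patients will have swabs, but not undergo randomization". A baseline carrier can therefore be randomized at months 0, 6, 12 and 18.
- Local carriers are also swabbed every 28 days. "Those who have repeat positive colonization swabs during this initial 6 month follow-up period will be observed", so these swabs do not trigger a new assignment.

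Section VII gives no time origin for patients who start positive, no censoring at re-randomization and no regrouping. The unique-randomization analysis (Sections 3.1 and VII) uses each subject's first randomization only. It is attached to the primary endpoint and is not linked to question (4).

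**The concern.** The quantity of interest is time spent negative, but both treated groups begin positive. Two clocks fit the text:

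- **Clock A:** from the first negative swab to the next positive one. Clearance is then entry to the risk set, and many patients may enter only after a later course.
- **Clock B:** from the first randomization to the first later positive swab.

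Under clock A with the initial group kept, a patient who stays positive on placebo, is re-randomized to active and then clears contributes negative time to the placebo group. The two curves would be pulled together even if the drug works as assumed, and the placebo curve could be misread as the course of untreated carriage. An analyst could choose between the clocks after seeing the data.

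A second loss occurs under either clock. A patient who starts negative and is first randomized at month 6, 12 or 18 sits in the initially negative group and adds nothing to active v placebo.

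**Working it through.** **Inputs.** The sample-size text in Section VII assumes that "85% in the non-treatment arm would remain colonized versus 7-39% (mean 23%) of the treated would remain colonized". Re-randomization is 1:1 among those positive at months 6, 12 and 18 (Section 6.3).

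**The plan's own figure.** No figure is given for question (4). The colonization table does reproduce from these rates. Let d = 0.85 - p and p̄ = (0.85 + p)/2. Then n = [1.96√(2p̄(1-p̄)) + 0.842√(0.85×0.15 + p(1-p))]²/d², with continuity correction n/4 × [1 + √(1 + 4/(nd))]². For p = 0.07, 0.23 and 0.39 this gives 7.4, 11.9 and 20.4, rounded up to 8, 12 and 21 carriers per arm. Dividing by the 10% colonization rate gives 80, 120 and 210, as stated.

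**Assumptions for the check.** The rates apply to every 6-month period, are the same for repeat courses and all patients, swabs are 6-monthly only, and nobody re-acquires MRSA.

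**Clock A, initial-placebo group, treated rate 0.23** (first clearances, as fractions of the group):

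| By month | Still positive at start of period | After active | After placebo |
|---|---|---|---|
| 6 | 1.000 | 0 | 0.150 |
| 12 | 0.850 | 0.425 × 0.77 = 0.327 | 0.425 × 0.15 = 0.064 |
| 18 | 0.459 | 0.2295 × 0.77 = 0.177 | 0.2295 × 0.15 = 0.034 |
| 24 | 0.248 | 0.124 × 0.77 = 0.095 | 0.124 × 0.15 = 0.019 |
| Total | | 0.599 | 0.267 |

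Share after an active course = 0.599/(0.599 + 0.267) = 69%. The same recursion over the plan's range gives:

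| Treated rate | By month 12 | By month 18 | By month 24 |
|---|---|---|---|
| 0.07 | 65% | 70% | 72% |
| 0.23 | 60% | 67% | 69% |
| 0.39 | 55% | 62% | 65% |

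A patient first negative at month 24 has no follow-up left, so month 18 is the relevant column for time at risk.

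**Size of the dilution.** In the initial-active group at 0.23, the share of first clearances by month 18 that follow an active course is 0.906/(0.906 + 0.027) = 97%. The two groups therefore differ by 97 - 67 = 30 points in the course that preceded clearance, where a clean comparison would differ by 100 (29 points at 0.07, 32 at 0.39).

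The gap in never having cleared shrinks likewise. After month 6 each group's fraction is multiplied by (0.23 + 0.85)/2 = 0.54 per period. The gap is 0.85 - 0.23 = 62 points at month 6, then 62 × 0.54 = 33, 18 and 10 points at months 12, 18 and 24.

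**Clock B.** Re-randomization at a 6-month visit requires a positive swab. That swab, if not an earlier one, is already the event. No first event can follow a re-randomization, and a simulation with 6-monthly swabs found none.

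**Sensitivity to the 28-day swabs.** These give local placebo carriers extra chances of a first negative before month 6. The documents do not say how many would have one. As an assumption, double the placebo chance per period from 15% to 30% and hold active at 77%. The retention factor is 1 - (0.30 + 0.77)/2 = 0.465. After active: 0.70 × 0.385 × (1 + 0.465 + 0.216) = 0.453. After placebo: 0.30 + 0.70 × 0.15 × 1.681 = 0.477. The month-24 share falls to 0.453/0.930 = 49%.

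**The case against.** A reader might infer that the plan keeps the initial treatment group for the whole study, so that the placebo curve is mostly made of active-drug clearances. The documents do not support that. In the group labels, the word initially describes colonization status. Keeping the first assignment throughout is an inference from silence. The Kaplan-Meier event is acquiring MRSA, so clearances are not events on the planned curve. Under clock B the problem is absent. All of this stands, and it is why the finding is conditional.

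It is also fair that question (1) carries the main treatment comparison and pools the 6-monthly data, that the sample size is for proportions, and that the shares ignore the 28-day swabs and so overstate the effect for local patients. Power figures for clock A would need relapse rates after clearance, which the documents do not give, so none are offered here.

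The objection does not remove the gap. Clock B avoids the dilution only if it is chosen, and the plan does not choose it. Time spent negative fits clock A at least as naturally for patients who begin positive.

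**Conclusion.** The point holds in conditional form. Question (4), one of four primary questions, does not define time zero or the handling of re-randomization for patients who start positive. Under the first-negative clock with initial groups kept, about 65-72% of first clearances in the initial-placebo group by month 24 follow an active course (62-70% by month 18), and the exposure contrast is about 30 points where it should be 100. Under the first-randomization clock there is no such dilution.

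The figures rest on constant per-period rates, 6-monthly swabs, no re-acquisition and no differences between patients. The majority share is not robust to a much higher chance of a first negative swab on placebo. The separate loss of patients first randomized after baseline holds under either clock; its size cannot be given, because the protocol does not split its 50-55 expected randomized participants by visit. The trial's main comparison in question (1) is not affected by this point.

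**What to change.** Reword question (4) as follows:

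- Each randomization is its own record, grouped by the assignment made then, whether at baseline or later.
- Time zero is that randomization.
- The event is the first MRSA-positive surveillance swab after the treatment course.
- Follow-up ends at the event, the next randomization or month 24. No time after a re-randomization counts for the earlier assignment.
- Active v placebo is compared with a patient-clustered (robust) variance.
- A first-randomization-only version is reported as the unique-randomization sub-analysis already planned.

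The initially negative curve can remain as a separate description.

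The cost is plan wording and some programming, with no new patients, visits or swabs. There are two limits. Persistent carriers have only about 6 months under any one assignment, so their curves cannot run to month 24. On this clock an early event mixes failure to clear with re-acquisition. Time negative among those who cleared can be shown beside it by the assignment in force, labelled as descriptive because clearing happens after randomization.

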3.2 Secondary Objectives

- a. To determine the prevalence and incidence of MRSA colonization of the nares, throat, perirectal, axilla, and groin areas among HIV infected patients and to study changes in the colonization rates over time.
- b. To determine the predictors of MRSA colonization and infection among HIV-infected persons including examination of demographics, sexual activity, hygienic practices, drug use, antibiotic and antiretroviral medications, sexually transmitted diseases, and HIV control.
- c. To evaluate the change in CD4 counts and HIV viral loads during the time of a MRSA or soft tissue infection.
- d. To characterize the molecular characteristics and the antimicrobial sensitivities of MRSA isolates in this population.
- e. To continue the previous retrospective study of MRSA infections among HIV-infected persons to examine the incidence of and describe the clinical features of MRSA infections and their response to treatment among HIV-infected patients seen within the HIV clinic at NMCSD. This study also will continue to compare those with and without MRSA infections in terms of demographic data, HIV viral loads, CD4 counts, and use of medications including antiretroviral and antimicrobial agents.

IV. BACKGROUND AND SIGNIFICANCE

MRSA was first recognized in 1961 and subsequently became a frequent cause of infections within the hospital setting. The first community-acquired MRSA infections occurred in the early 1980s. Within the past several years, the number of community-acquired MRSA cases has dramatically increased with incidence rates of 18 to 26 cases per

100,000 persons [1, 2]. In addition to individual cases, numerous outbreaks have occurred among prison inmates, athletes, military trainees, and men who have sex with men (MSM) [14-18].

Patients presenting with community-acquired MRSA infections typically present with skin or soft tissue infections such as folliculitis, furuncles, carbuncles, abscesses, or cellulitis [1, 7]. Despite that most of these infections occur in young, otherwise healthy individuals, community-acquired MRSA infections have led to a high hospitalization rate with up to 25% requiring admission for the management of the MRSA infection [1].

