HIV infection is a known risk factor for both MRSA colonization and infection [7, 8, 11]. A recent study showed that community-acquired MRSA increased six-fold among HIV-infected persons during the years 2000 to 2003 [7]. Risk factors for community-acquired MRSA among HIV-infected patients cited in the literature include a history of MSM or intravenous drug use as the patient's HIV transmission risk factor, a low current CD4 count, high HIV viral load, and the absence of trimethoprim-sulfamethoxazole (TMP/SMX) prophylaxis [7]. Other studies found an association with exposure to public hot tubs/saunas, having a sex partner with a skin infection, and prior beta-lactam

antibiotics [13, 25]. Colonization with MRSA among HIV infected persons has been linked to low CD4 count (<100 cells/mm³), lack of TMP/SMX prophylaxis, recent antibiotic use, and hospitalizations [26, 27].

A retrospective case-control study was performed including the years of 1993-2005 among 425 HIV patients seen at the Naval Medical Center San Diego (NMCSD), of whom, 25 (5.9%) patients were found to be infected with community-acquired MRSA. All cases occurred after 2002, with a 17-fold increase from 2003 to 2005 (Chi-square test of trend 15.7, p<0.001). The annual incidence during the year 2005 among our HIV patients was 40 cases/1000 person-years compared to 2.28 cases/1000 person-years (or 741 cases/325,000) among HIV-negative persons (18-fold higher rate). In the univariate analyses, lower current CD4 count, CDC stage C vs. A, history of syphilis, and exposure to beta-lactam antibiotics in the past year were predictive of MRSA. In the multivariate model, history of syphilis and exposure to beta-lactam antibiotics remained as significant predictors [12].

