6.3 Active Surveillance & Clinic Assessments

Each study participant will be seen a minimum of five times over the 24-month study period by a study physician or study team member at the clinic (baseline visit and every six months (+/- 2 months) for a two year period). The maximum number of visits depends on if the patient has repeated infections or colonization for MRSA; this will likely not exceed 12 visits during the 2 year study period. This includes Visit 1 to sign the informed consent and register subject with DCC (assigned a PIN). Women of childbearing age will undergo a urine pregnancy test to assure that she meets inclusion/exclusion criteria. Enrolled patients will fill out questionnaires including data on prior MRSA or soft tissue infections, recent hospitalizations, demographic information (age, race, sex), substance use (alcohol, tobacco and illicit drugs), current and recent (within the past 12 months) antibiotics, current receipt of highly active antiretroviral therapy (HAART), contact with persons with a history of soft tissue infections and/or MRSA, relative or contact who works in the healthcare setting, exercise habits, sexual activities, sexually transmitted diseases, and activities previously associated with MRSA including sports, use of public baths/saunas, and hygienic practices (refer to case report forms). Each participant will have swabs of their nares, throat, axilla, groin, and perirectal area obtained for determining MRSA or MSSA colonization. Study coordinators will examine the patient's medical records and the hospital computer database for medication use, medical conditions including MRSA or soft tissue infections, hospitalizations, sexually transmitted diseases, and HIV data including CD4 count, HIV viral loads, and CDC staging.

During regular study visits 2, 3, 4, and 5, patients will have repeated swabs, questionnaires and review of their medical record which occurs every six months (+/- 2 months). The study duration for each participant is 24 months.

Patients will have the following swabs to detect colonization of MRSA or MSSA performed:

[figure not shown]
- one swab of both nares;
- one swab of the throat
- one swab of the bilateral groin areas;
- one swab of the axilla areas; and
- one swab of the perirectal area.

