10.3 Planning and Use for Storage of Biological Specimens

All blood drawn for HIV viral loads, CD4 counts, complete blood counts, or blood cultures will be destroyed after the test is performed at the local laboratory site with no storage of any blood samples. This is the local standard of the individual laboratories participating in this study.

Isolates identified to be MRSA or MSSA at the individual participating sites will be stored at -70°C in the local microbiology laboratory. Periodically, these specimens will be mailed frozen via Federal Express using proper labeling for biological specimens to the Naval Medical Center San Diego. Specimens will be shipped to the laboratory at SAMMC in Texas for molecular characterization. These specimens do not contain any of the patients' cells or genetic material, but rather our bacteria isolated from clinical specimens.

XI. TIME REQUIRED TO COMPLETE

Enrollment will take approximately 30 months. Another 24 months will be required to complete all of the study visits and 6 months for data analyses. Total study time is approximately 60 months.

XII. NUMBER OF SUBJECTS TO BE STUDIED

The study population will consist of a total of 550 volunteers.

XIII. NUMBER OF CHARTS TO BE REVIEWED

Medical charts will be reviewed on an ongoing basis by five collaborative research sites until 550 participants have been enrolled. Charts from all HIV-infected patients in the HIV clinic at NMCSD will be reviewed for the retrospective cohort.

XIV. FUNDING IMPLICATIONS

Required resources from NIH/NIAID will be provided by the Henry M. Jackson Foundation (HJF), through a cooperative agreement between the HJF and the NIH/NIAID. There will be no funding from outside resources. See attached budget.

XV. DATE PREPARED

May 20, 2006
Revised September 20, 2006; Version 1.0
Revised April 23, 2007; Version 1.1
Revised November 21, 2008; Version 1.2

Revised February 26, 2009; Version 1.3
Revised May 29, 2009; Version 1.4
Revised November 15, 2010; Version 2.0
Revised February 10, 2011; Version 3.0
Revised July 20, 2011; Version 4.0
Revised September 1, 2011; Version 5.0
Revised May 25, 2012; Version 6.0

XVI. BIBLIOGRAPHY

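### Incidence for secondary objective (a) has no person-time denominator: applied literally to staggered entry the formula understates the rate about 2.25-fold, and the wording leaves open a reading with only a 5 to 10% error

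*Combined protocol and SAP*

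**What the plan says.** Section 3.2(a) sets out to estimate the prevalence and incidence of MRSA colonization and "to study changes in the colonization rates over time". In Section VII, the analysis for this objective takes prevalence as the number colonized at the start over the total population, and "the incidence as the number of new infections per calendar time divided by the total population studied". No person-time denominator is given for this objective anywhere.

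On timing, Section XI states: "Enrollment will take approximately 30 months. Another 24 months will be required to complete all of the study visits". It adds six months for analysis and concludes: "Total study time is approximately 60 months". Section 5.2 describes enrollment as continuous up to 550 participants. Section 6.3 states: "The study duration for each participant is 24 months". Section VII allows for 50 drop-outs and plans to examine prevalence and incidence about once a year.

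Person-years appear only in the background rates. Section IV reports that the 2005 incidence among the San Diego clinic's HIV patients "was 40 cases/1000 person-years compared to 2.28 cases/1000 person-years" among HIV-negative persons. Section VII cites about 13 per 1,000 person-years from another HIV cohort. The Precis (Section I) and Section IV both describe the study's own incidence as covering a two-year period, a time base that the Section VII definition does not use.

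**The concern.** With entry spread over 30 months and 24 months of follow-up each, no calendar period has all 550 participants under observation for its whole length. Some have not yet entered and others have finished. A formula that counts events per unit of calendar time and divides by everyone studied therefore credits observation time that never took place. The rate comes out too low, by an amount that depends on how much of the cohort is present in the period.

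Two things are at stake. The overall rate would not be on the person-year scale of the 13 and 40 per 1,000 that the protocol uses as background. A calendar-year series, which the yearly examination makes likely, would partly trace the enrollment curve rather than MRSA.

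The definition also counts infections, whereas objective (a) concerns colonization. Participants already colonized at baseline stay in the denominator although they cannot newly acquire colonization.

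**Working it through.** **Inputs.** N = 550 (Sections 5.2 and XII); accrual 30 months, then 24 months to finish visits (Section XI); follow-up 24 months each (Section 6.3); 50 drop-outs (Section VII); illustrative rates of 13 and 40 per 1,000 person-years (Sections VII and IV). Uniform accrual is my assumption and is used only for the calendar-year profile.

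**The plan's own figure.** 30 + 24 + 6 = 60 months, as Section XI states. Observation occupies 30 + 24 = 54 months, or 4.5 years. The documents state no planned incidence or person-time for this objective, so there is nothing further to reproduce.

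**Whole study, literal reading.**
- Time implied by the formula: 550 × 4.5 = 2,475 person-years.
- Time observed with full follow-up: 550 × 2 = 1,100 person-years.
- Ratio: 2,475 / 1,100 = 2.25, whatever the accrual pattern within the 30 months.
- Drop-outs each contributing half their follow-up: 500 × 2 + 50 × 1 = 1,050, ratio 2.36. Contributing nothing: 1,000, ratio 2.48.
- A true 40 per 1,000 person-years gives 44 infections in 1,100 person-years and would be reported as 44 / 2,475 = 17.8 per 1,000 per year. A true 13 gives 14.3 infections, reported as 5.8.

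**By calendar year, uniform accrual, no drop-out.** The number under observation at t years is 550 × [min(t/2.5, 1) − min(max(t − 2, 0)/2.5, 1)]. It peaks at 440. Person-years are this number integrated over each period. The share of the true rate reported is person-years divided by (denominator × period length).

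| Period | Person-years | Share, denominator 550 | True 40 reads as | Enrolled to date | Share | True 40 reads as |
|---|---|---|---|---|---|---|
| Year 1 | 110 | 0.20 | 8 | 220 | 0.50 | 20 |
| Year 2 | 330 | 0.60 | 24 | 440 | 0.75 | 30 |
| Year 3 | 412.5 | 0.75 | 30 | 550 | 0.75 | 30 |
| Year 4 | 220 | 0.40 | 16 | 550 | 0.40 | 16 |
| Last half-year (annualized) | 27.5 | 0.10 | 4 | 550 | 0.10 | 4 |

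The person-years sum to 1,100. A constant rate rises and then falls under either denominator, but the rise is smaller with those enrolled to date.

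**Participant-time reading.** If the time base is each participant's own two years, the formula implies 550 × 2 = 1,100 person-years. The ratio is 1.0 with full follow-up, 1,100 / 1,050 = 1.05 if drop-outs contribute half, and 1,100 / 1,000 = 1.10 if they contribute nothing.

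**New colonization.** If 10 to 15% are colonized at baseline (the range in Section 5.2), keeping them in the denominator adds a further factor of 1/0.90 = 1.11 to 1/0.85 = 1.18.

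**The case against.** The 2.25 depends on one reading of loose words. It requires the calendar term to mean the study's 54-month span and the population to be all 550 throughout. The Precis and Section IV point instead to a two-year period. In the same sentence, prevalence at the start of the study makes sense under continuous enrollment only as each participant's own baseline, so the incidence term may also be meant in participant time.

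The protocol also moves freely between the two scales. Section IV equates 2.28 per 1,000 person-years with 741 cases in 325,000 people, and Section VII restates the clinic's 40 as a rate per 1,000 persons in the year 2005. At a yearly look before enrollment ends, 550 could not be the denominator. The trend wording in Section 3.2(a) concerns colonization, which is swabbed at fixed study months, while the formula counts infections. No formal comparison with the clinic's rate is planned.

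Most of this stands. A reader might infer that the plan will certainly understate incidence 2.25-fold and show a spurious rise and fall. The documents do not support that: the first needs the literal calendar reading, and the second also needs reporting by calendar period and an accrual pattern that the protocol does not give.

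The objection does not remove the ambiguity. Calendar time is what the definition says, no other passage supplies a denominator, and a rise and fall remains when those enrolled to date are used.

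**Conclusion.** The concern holds as a defect of definition. Two analysts following Section VII could report rates that differ more than two-fold. Depending on the reading and on how long drop-outs stay, the understatement runs from about 1.05-fold (participant time, drop-outs contributing half) to about 2.5-fold (literal calendar time, drop-outs contributing nothing). With full follow-up the two ends are 1.0 and 2.25.

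The pattern of 8, 24, 30 and 16 per 1,000 is conditional on a true constant 40, uniform accrual, calendar-year reporting and a fixed denominator of 550. With those enrolled to date, year 1 would read 20.

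This is a descriptive secondary objective with no test or sample size attached. The randomized comparison is unaffected and the denominator can be put right at analysis. The change should be made, but it does not threaten the trial's primary conclusion.

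**What to change.** Replace the definition in Section VII with new events divided by person-years under observation and at risk, counted from enrollment to withdrawal or month 24. For any calendar-period rate, including the yearly examinations, use the person-years observed in that period. Report per 1,000 person-years with a confidence interval.

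State the event rule explicitly, because the sample-size text in Section VII counts new infections as separate events and stopping the clock at the first event would silently drop the repeats:
- First events: time censored at the event.
- All infections, counting repeats: time not censored at an event, with an interval that allows for correlation within a person.
- New colonization: computed separately from infection, among those not colonized at baseline.

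The cost is a few sentences in Section VII and minor extra analysis. The dates needed should come from the enrollment visit, the scheduled and infection visits, and the completion/discontinuation form, so no design change or new data collection is required.
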